**Appendix 5: International Myeloma Working Group Uniform Response Criteria (2016)**

Relapse Subcategory	Relapse Criteria
Relapse from CR (to be used only if the endpoint studied is PFS) c	
Any one or more of the following:
 
 
• Reappearance of serum or urine M-protein by immunofixation or electrophoresis
 
• Development of <math>\geq 5\%</math> plasma cells in the BM
 
• Appearance of any other sign of progression (i.e., new plasmacytoma, lytic bone lesion, or hypercalcemia)
 

BM=bone marrow; CR=complete response; CT=computed tomography; FLC=free light chain; M-protein=monoclonal protein; MR=minimal response; MRI=magnetic resonance imaging; PD=progressive disease; PET=positron emission tomography; PFS=progression-free survival; PR=partial response; sCR=stringent complete response; SD=stable disease; SPD=sum of the products of diameters; VGPR=very good partial response.

- a Special attention should be given to the emergence of a different M-protein following treatment, especially in the setting of patients having achieved a conventional CR, often related to oligoclonal reconstitution of the immune system. These bands typically disappear over time, and in some studies, have been associated with a better outcome. Also, appearance of IgGk in patients receiving monoclonal antibodies should be differentiated from the therapeutic antibody.
- b In some cases it is possible that the original M-protein light-chain isotype is still detected on immunofixation, but the accompanying heavy-chain component has disappeared; this would not be considered a CR even though the heavy-chain component is not detectable, since it is possible that the clone evolved to one that secreted only light chains. Thus, if a patient has IgA lambda myeloma, then to qualify as a CR there should be no IgA detectable on serum or urine immunofixation; if free lambda is detected without IgA, then it must be accompanied by a different heavy-chain isotype (IgG, IgM, etc.). Modified from Durie et al. 2006. Requires two consecutive assessments to be carried out at any time before the institution of any new therapy (Durie et al. 2015).
- c Plasmacytoma measurements should be taken from the CT portion of the PET/CT or MRI scans, or dedicated CT scans where applicable. For patients with only skin involvement, the skin lesions should be measured with a ruler. Measurement of tumor size will be determined by the SPD.
- d Positive immunofixation alone in a patient previously classified as achieving a CR will not be considered progression. Criteria for relapse from a CR should be used only when calculating disease-free survival.
- e In the case where a value is felt to be a spurious result per investigator discretion (e.g., a possible laboratory error), that value will not be considered when determining the lowest value.
- f CRAB features=calcium elevation, renal failure, anemia, lytic bone lesions.

**Appendix 6**  
**Modified Cockcroft–Gault Equation (Using Ideal Body Mass Instead of Mass)**

$$eCCr = \frac{(140 - \text{Age}) \cdot \text{IBM (kg)} \cdot [0.85 \text{ if female}]}{72 \cdot \text{serum creatinine (mg/dL)}}$$

Or, if serum creatinine is in  $\mu\text{mol/L}$ :

$$eCCr = \frac{(140 - \text{Age}) \cdot \text{IBM (kg)} \cdot [1.23 \text{ if male, } 1.04 \text{ if female}]}{\text{serum creatinine } (\mu\text{mol/L})}$$

(IBM) should be used:

$$\text{IBM (kg)} = [(\text{height in cm} - 154) \times 0.9] + (50 \text{ if male, } 45.5 \text{ if female})$$

eCCR = estimated creatinine clearance; IBM = ideal body mass.

## **Appendix 7**

### **Recommended Anaphylaxis Management**

These guidelines are intended as a reference and should not supersede pertinent local or institutional standard operating procedures.

**The following equipment is needed in the event of a suspected anaphylactic reaction during study drug infusion:**

- Appropriate monitors (ECG, blood pressure, pulse oximetry)
- Oxygen and masks for oxygen delivery
- Airway management devices per standard of care
- Epinephrine for intravenous, intramuscular, and/or endotracheal administration in accordance with institutional guidelines
- Salbutamol (or albuterol or equivalent)
- Antihistamines (H1 and H2 blockers)
- Corticosteroids
- IV infusion solutions, tubing, catheters, and tape

**The following are the procedures to follow in the event of a suspected anaphylactic reaction during study drug infusion:**

- Stop the study drug infusion.
- Call for additional assistance.
- Maintain an adequate airway.
- Provide oxygen.
- Ensure that appropriate monitoring is in place, with continuous ECG and pulse oximetry monitoring, if possible.
- Administer epinephrine first, followed by antihistamines, albuterol, or other medications as required by patient status and directed by the physician in charge.
- Continue to observe the patient and document observations.

## Appendix 8

### Examples of Sensitive In Vivo CYP Substrates and CYP Substrates with Narrow Therapeutic Range

CYP Enzymes a	Sensitive Substrates b	Substrates With Narrow Therapeutic Range c
CYP1A2	Alosetron, caffeine, duloxetine, melatonin, ramelteon, tacrine, tizanidine	Theophylline, tizanidine
CYP2B6 d	Bupropion, efavirenz	
CYP2C8	Repaglinide e	Paclitaxel
CYP2C9	Celecoxib	Warfarin, phenytoin
CYP2C19	Lansoprazole, omeprazole, S-mephenytoin	S-mephenytoin
CYP3A f	Alfentanil, aprepitant, budesonide, buspirone, conivaptan, darifenacin, darunavir, dasatinib, dronedarone, eletriptan, eplerenone, everolimus, felodipine, indinavir, fluticasone, lopinavir, lovastatin, lurasidone, maraviroc, midazolam, nisoldipine, quetiapine, saquinavir, sildenafil, simvastatin, sirolimus, tolvaptan, tipranavir, triazolam, vardenafil	Alfentanil, astemizole, g cisapride, g cyclosporine, dihydroergotamine, ergotamine, fentanyl, pimozone, quinidine, sirolimus, tacrolimus, terfenadine g
CYP2D6	Atomoxetine, desipramine, dextromethorphan, metoprolol, nebivolol, perphenazine, tolterodine, venlafaxine	Thioridazine

AUC = area under the concentration–time curve.

- a Note that this is not an exhaustive list. For an updated list, see the following link: <https://www.fda.gov/Drugs/DevelopmentApprovalProcess/DevelopmentResources/DrugInteractionsLabeling/ucm080499.htm>.
- b Sensitive CYP substrates refer to drugs whose plasma AUC values have been shown to increase 5-fold or higher when co-administered with a known CYP inhibitor.
- c CYP substrates with narrow therapeutic range refers to drugs whose exposure-response relationship indicates that small increases in their exposure levels by the concomitant use of CYP inhibitors may lead to serious safety concerns (e.g., Torsades de Pointes).
- d The AUC of these substrates were not increased by 5-fold or more with a CYP2B6 inhibitor, but they represent the most sensitive substrates studied with available inhibitors evaluated to date.
- e Repaglinide is also a substrate for OATP1B1, and it is only suitable as a CYP2C8 substrate if the inhibition of OATP1B1 by the investigational drug has been ruled out.
- f Because a number of CYP3A substrates (e.g., darunavir, maraviroc) are also substrates of P-gp, the observed increase in exposure could be due to inhibition of both CYP3A and P-gp.
- g Withdrawn from the United States market because of safety reason.

## Appendix 9 Modified Cytokine-Release Syndrome Grading System

Source: Lee et al. 2019.

Grade a	Toxicity
Grade 1	Fever $\geq 38^{\circ}\text{C}$ with or without constitutional symptoms
Grade 2	Fever $\geq 38^{\circ}\text{C}$ with either: Hypotension – responding to fluids but not requiring vasopressors Hypoxia – requiring low-flow nasal cannula ( $\leq 6$ L/min) or blow-by oxygen to maintain oxygen saturation Organ toxicity: b Grade 2
Grade 3	Fever $\geq 38^{\circ}\text{C}$ with either: Hypotension – requiring single vasopressor (with or without vasopressin) Hypoxia – requiring high flow nasal cannula ( $> 6$ L/min), facemask, non-rebreather mask, or Venturi mask to maintain oxygen saturation Organ toxicity: b Grade 3 organ toxicity or Grade 4 transaminitis
Grade 4	Fever $\geq 38^{\circ}\text{C}$ with either: Hypotension – requiring multiple vasopressors (excluding vasopressin) Hypoxia requiring positive pressure (e.g., CPAP, BiPAP, intubation and mechanical ventilation) Organ toxicity: b Grade 4 (excluding transaminitis)
Grade 5	Death

CRS = cytokine-release syndrome.

a CRS grade is determined by the more severe event: hypotension or hypoxia not attributable to any other cause (e.g., if a patient has a temperature of  $39^{\circ}\text{C}$ , is on 4 L/min of oxygen by nasal cannula, and has hypotension requiring the use one vasopressor, this would be considered Grade 3 CRS).

b Organ toxicities associated with CRS may be graded according to NCI CTCAE v5.0.

## **Appendix 10**

### **Management Guidelines for Cytokine-Release Syndrome**

Guidelines for management of CRS are summarized in [Table 1](#) below based on the modified grading scale as described in [Appendix 9](#). Management of Grade  $\geq 3$  IRR and/or CRS should be immediately discussed with the Medical Monitor. As noted below, even moderate presentations of CRS in patients with extensive comorbidities should be monitored closely with consideration given to intensive care unit admission and therapeutic intervention.

Refer to Section [5.3.5.1](#) for adverse event reporting procedures related to IRR and CRS.

**Appendix 10: Management Guidelines for Cytokine Release Syndrome**

**Table 1 Management Guidelines for Cytokine-Release Syndrome**

Toxicity a	Action to Be Taken

Grade 1 Fever b ≥ 38°C with or without constitutional symptoms (such as: nausea, fatigue, headache, myalgia, malaise)
	
Immediate actions:
 
 
• If infusion still ongoing, slow the infusion rate up to 50% or interrupt infusion.
 
• Treat symptomatically as indicated, including antihistamines, antipyretics, and/or analgesics as needed.
 
• Treat fever and neutropenia if present.
 
• Monitor fluid balance; administer IV fluids as clinically indicated.
 
 
Restarting infusion:
 
 
• If study medication infusion was interrupted, wait until 30 minutes after the event has resolved before restarting the infusion at 50% of the original infusion rate.
 
 
Next cycle:
 
 
• Pretreat with antihistamines and antipyretics/NSAIDS.
 

Grade 2 Fever b ≥ 38°C with either: Hypotension - responding to fluids but no required vasopressor and/or Hypoxia – requiring ≤ 6 L/min by nasal cannula or blow-by to maintain oxygen saturation Organ toxicity: Grade 2
	
Immediate actions:
 
 
• Follow all Grade 1 recommendations.
 
• Hold further study medication treatment until symptoms completely resolved.
 
• Consider treatment with IV corticosteroids (methylprednisolone 2 mg/kg/day or, if neurologic symptoms are present, dexamethasone 10 mg).
 
• Consider administering cytokine therapy.
 
• Monitor cardiac and other organ function closely.
 
• Provide hemodynamic support as indicated.
 
• Provide oxygen for hypoxia.
 
• Admit to ICU as appropriate.
 
• If no improvement within 24 hours, manage as a Grade 3 event:             
 
– Notify Medical Monitor.
 
– Initiate work-up and assess for signs and symptoms of MAS/HLH. c
 
– May receive the next dose of study medication if symptoms resolve to Grade ≤ 1 for 3 consecutive days with approval of Medical Monitor.
 
 
 

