## **4.4.3            Prohibited Therapy**

Use of the following concomitant therapies is prohibited as described below:

- Investigational therapy (other than protocol-mandated study treatment) for various time periods prior to starting study treatment, depending on the agent (see Section [4.1.2](#)) and during study treatment
- Concomitant therapy intended for the treatment of cancer (including, but not limited to, chemotherapy, immunotherapy, radiotherapy, and herbal therapy) for various time periods prior to starting study treatment, depending on the agent (see Section [4.1.2](#)), and during study treatment, until disease progression is documented and the patient has discontinued study treatment, with the exception of palliative radiotherapy and local therapy under certain circumstances (see Section [4.4.1](#) for details)
- Hormone therapy for the treatment of cancer, whether approved by local regulatory authorities or investigational
  - Adjuvant endocrine therapy for non-metastatic prostate cancer and non-metastatic, hormone-receptor positive breast cancer is permitted.
- Biologic agents other than hematopoietic growth factors, which are allowed if clinically indicated and used in accordance with instructions provided in the package inserts
- Any therapies intended for the treatment of MM, whether approved by local regulatory authorities or investigational

- Live, attenuated vaccines

Patients who require the use of any of these agents will be discontinued from treatment with RO7297089. Patients who are discontinued from study treatment will be followed for safety outcomes for 90 days following the patient's final dose of RO7297089 or until the patient receives another anti-cancer therapy, whichever occurs first.

The above list of medications is not necessarily comprehensive. The investigator should contact the Medical Monitor if questions arise regarding medications not listed above.

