**Appendix 10: Management Guidelines for Cytokine Release Syndrome**

**Table 1 Management Guidelines for Cytokine-Release Syndrome (cont.)**

Event a	Action to Be Taken
Grade 2 (cont.)	
Restarting infusion:
 
 
• Wait until 30 minutes after the event has resolved before restarting the infusion at up to 25% of the original infusion rate.
 
• If hypotension or hypoxia recurs, stop infusion immediately. Study medication should not be re-administered (re-started) again during this cycle.               
 
– If hypotension or hypoxia recurs, manage as a Grade 3 event.
 
 
 
 
Next cycles:
 
 
• May receive the next dose of study medication if symptoms resolve to Grade <math>\leq</math> 1 for 3 consecutive days with approval of Medical Monitor, as follows:               
 
– Pretreat with antihistamines, antipyretics and/or analgesics as clinically indicated.
 
– Pretreat with IV corticosteroids (methylprednisolone 80 mg or dexamethasone 16 mg) at least 60 minutes prior to the administration of study medication
 
– Administer study medication at 50% of the initial infusion rate of the previous cycle.
 
 
 
 
Subsequent cycles:
 
 
• If there is an occurrence of IRR or CRS Grade <math>\geq</math> 3 in any of the subsequent cycles, permanently discontinue study medication regardless of recovery (see Grade 3 management guidelines).
 
• If there is an occurrence of a Grade <math>\leq</math> 2 CRS in subsequent cycles, manage as indicated by severity (see Grade 1 or Grade 2 management guidelines).
 

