**Appendix 10: Management Guidelines for Cytokine Release Syndrome**

**Table 1 Management Guidelines for Cytokine-Release Syndrome (cont.)**

Grade a	Action to Be Taken

Grade 3
 
Fever b ≥ 38°C with either:  Hypotension – requiring a single vasopressor (with or without vasopressin) and/or  Hypoxia – requiring > 6 L/min oxygen by nasal cannula, facemask, non-rebreather mask, or Venturi mask to maintain oxygen saturation
 
Organ toxicity: Grade 3 organ toxicity or Grade 4 transaminitis
	
Immediate actions:
 
 
• Stop further infusion of study medication
 
• Admission to ICU is recommended
 
• Treat symptomatically as indicated, including antihistamines, antipyretics, and/or analgesics as needed.
 
• Provide other supportive care as clinically indicated (e.g., fever and neutropenia, infection).
 
• Monitor fluid balance; administer IV fluids as clinically indicated.
 
• Treat with IV corticosteroids (methylprednisolone 2 mg/kg/day or, if neurologic symptoms are present, dexamethasone 10 mg).
 
• Consider anti-cytokine therapy.
 
• Monitor cardiac and other organ function closely.
 
• Provide oxygen for hypoxia.
 
• Notify Medial Monitor.
 
• Initiate work-up and assess for signs and symptoms of MAS/HLH. c
 
 
Restarting infusion:
 
 
• Study medication should not be administered again during this cycle.
 

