**Appendix 10: Management Guidelines for Cytokine Release Syndrome**

**Table 1 Management Guidelines for Cytokine-Release Syndrome (cont.)**

Grade a	Action to Be Taken
Grade 3 (cont.)	
Next cycle:
 
 
• If the patient had a Grade <math>\geq</math> 2 IRR or CRS in any previous cycle, permanently discontinue study medication.
 
• If patient does not recover (is febrile or still on vasopressors) within 8 hours after corticosteroid and anti-cytokine treatment, permanently discontinue study medication.
 
• If patient recovers (is afebrile and off vasopressors) within 8 hours following corticosteroid and anti-cytokine treatment, study medication can be administered in next cycle, as follows:               
 
– Pretreat with antihistamines, antipyretics and/or analgesics as clinically indicated.
 
– Pretreat with IV corticosteroids (methylprednisolone 80 mg or dexamethasone 16 mg) at least 60 minutes prior to the administration of study medication.
 
– Hospitalize patient for 24 hours.
 
– Administer study medication at 50% of the initial infusion rate of the previous cycle. d
 
 
 
 
Subsequent cycles:
 
 
• If a Grade <math>\geq</math>3 CRS recurs, permanently discontinue study medication.
 
• If there is an occurrence of a Grade <math>\leq</math> 2 CRS in subsequent cycles, manage as indicated by severity (i.e., Grade 1 or Grade 2 management guidelines).
 

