**Appendix 10: Management Guidelines for Cytokine Release Syndrome**

**Table 1 Management Guidelines for Cytokine-Release Syndrome (cont.)**

Grade a	Action to Be Taken

Grade 4
 
Fever b ≥ 38°C with either: Hypotension – requiring multiple vasopressors (excluding vasopressin) and/or Hypoxia – requiring positive pressure (e.g., CPAP, BiPAP, intubation and mechanical ventilation) Organ toxicity: Grade 4 (excluding transaminitis)
	
Immediate actions:
 
 
• Follow all Grade 3 management guidelines.
 
• Permanently discontinue study treatment.
 

CRS = cytokine-release syndrome; HLH = hemophagocytic lymphohistiocytosis; ICU = intensive care unit; MAS = macrophage activation syndrome.

- a Modified CRS grading per ASTCT (Lee et al. 2019). Refer to [Appendix 9](#) for the complete description of grading of symptoms.
- b Fever is defined as temperature ≥ 38°C not attributable to any other cause. In patients who have CRS and then receive antipyretic or anti-cytokine therapy such as tocilizumab or steroids, fever is no longer required to grade subsequent CRS severity. CRS grade is determined by the more severe event: hypotension or hypoxia not attributable to any other cause.
- c Refer to [Appendix 12](#) for HLH/MAS diagnostic criteria.
- d If the patient does not experience CRS during the next infusion at the 50% reduced rate, the infusion rate can be increased to the initial rate in subsequent cycles upon discussion with Medical Monitor. However, if this patient experiences another CRS event, the infusion rate should be reduced by 25%–50% depending on the severity of the event.

## Appendix 11

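### The Grade 2 row of the CRS management table lacks the prefix anti-, so read literally it reverses the treatment; a minor safety-text correction

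*Combined protocol and SAP*

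**What the plan says.** Sections 5.1.1.1 and 5.1.2.2 of the protocol refer sites to Appendix 10 for managing CRS. Table 1 of that appendix lists actions by grade. The wording on treatment directed at cytokines is as follows.

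- Grade 1: no such line.
- Grade 2, immediate actions: "Consider administering cytokine therapy".
- Grade 3, immediate actions: "Consider anti-cytokine therapy".
- Grade 3, next cycle, patient not recovered: "within 8 hours after corticosteroid and anti-cytokine treatment, permanently discontinue study medication".
- Grade 3, next cycle, patient recovered: "within 8 hours following corticosteroid and anti-cytokine treatment, study medication can be administered in next cycle".
- Grade 4: no line of its own; it says "Follow all Grade 3 management guidelines".
- Footnote b, on how fever counts toward grading once treatment has begun: it covers patients who "receive antipyretic or anti-cytokine therapy such as tocilizumab or steroids".

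The Grade 2 row also says when a case is to be handled as Grade 3. One trigger is no improvement within 24 hours. The other, under restarting the infusion, is "If hypotension or hypoxia recurs, manage as a Grade 3 event".

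**The concern.** The Grade 2 line names the opposite of what the rest of the table names. CRS is an excess of cytokines, and the drugs used against it block them. A line that tells the investigator to consider giving a cytokine is wrong in the unsafe direction, and it sits in operative safety text of a first-in-human trial.

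There is also a more ordinary consequence. Read as written, the Grade 2 row offers corticosteroids but no anti-cytokine rescue. A site that follows the table closely would find that option only on reaching Grade 3.

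Timing adds some weight. The introduction to Appendix 10 requires immediate discussion with the Medical Monitor only from Grade 3 upward, and the Grade 2 row calls for notification only after 24 hours without improvement. A site can therefore act on the faulty line before any required conversation with the sponsor.

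**Working it through.** No formula applies. The check is a count of mentions, a comparison of parallel lines, and a trace of which events reach the faulty row.

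**Count.** Mentions in Table 1 and its footnotes:

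- without the prefix: Grade 2 immediate actions, 1;
- with the prefix: Grade 3 immediate actions 1, Grade 3 next-cycle rules 2, footnote b 1, so 1 + 2 + 1 = 4.

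That is 1 of 5 without the prefix. Only the Grade 2 and Grade 3 rows have their own line among the immediate actions. One is wrong and the other is right.

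**Parallel lines.** In both rows the line comes directly after the corticosteroid line, which gives the same doses (methylprednisolone 2 mg/kg/day, or dexamethasone 10 mg with neurologic symptoms). In both it comes directly before the line on monitoring cardiac and other organ function. It is the same item in the same place, differing in the prefix. Footnote b is attached to the fever entry of the Grade 2 row itself and gives tocilizumab as an example. The intended word is not in doubt.

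**Other use of the phrase.** The exclusion criteria in Section 4.1.2 list cytokine therapy among systemic immunotherapeutic agents. So the unprefixed phrase has a different meaning elsewhere in this protocol. This does not show that a clinician would apply that meaning to a patient with CRS.

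**Which events meet the faulty row.**

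1. A first Grade 2 CRS event: yes.
2. A Grade 2 event with no improvement in 24 hours: moves to the Grade 3 row, which is correctly worded.
3. Low blood pressure or hypoxia returning after the infusion is restarted: also moves to the Grade 3 row.
4. A Grade 2 CRS event in a later cycle: the subsequent-cycle instructions, in both the Grade 2 and the Grade 3 rows, say to manage by severity. That leads back to the faulty row.
5. Grade 4: inherits the Grade 3 wording and is not affected.

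**The case against.** The strongest reply is that this is purely editorial. The item is introduced by a verb of consideration, names no drug and follows a line on corticosteroids. Footnote b on the same row spells out what is meant. No clinician treating CRS is likely to reach for a cytokine. Section 4.4.1 leaves supportive care to clinical need and local practice. CRS of any grade is an adverse event of special interest under Section 5.2.3, reportable within 24 hours, so the sponsor would hear of every case. Section 5.1.1.1 rates the likelihood of CRS as very low.

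Most of this stands, and it keeps the point minor. It does not remove the need for a correction. Rapid reporting tells the sponsor what happened but does not guide the first treatment decision, and nothing elsewhere in the documents corrects the Grade 2 line.

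Four further inferences are tempting but go too far.

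- A reader might infer that sites are likely to give cytokines to patients with CRS. The surrounding text makes the intended meaning plain.
- A reader might infer that any recurrent Grade 2 event moves to the correct row. The table says so only for hypotension or hypoxia after an infusion restart.
- A reader might take the infusion-related reactions described in Section 5.1.1.1 as evidence of how often this row will be used. They are reported there as infusion-related reactions, which have their own management table (Table 3 in Section 5.1.2.2), so they say nothing about use of the CRS row.
- A reader might look to Section 4.4.3, which prohibits most biologic agents, either as protection against misuse or as a bar to the intended rescue. That clause does not mention CRS treatment, and the documents do not say whether tocilizumab falls under it. Any tension exists already, because footnote b names tocilizumab and the Grade 3 row allows re-dosing after such treatment. It does not depend on the Grade 2 wording and is not part of this point.

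**Conclusion.** The point holds as a minor safety-text correction. One line in the Grade 2 CRS row has lost a prefix. Literally read, it reverses the treatment and leaves out the intended rescue option. It affects Grade 2 CRS events only, including those in later cycles, and only as an optional action. The chance of misuse is low. There is no effect on sample size, the dose-escalation model, dose decisions or any analysis.

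This rests on one assumption: that the prefix is missing from the signed protocol and was not lost when the file was converted to text. The second is unlikely, since the other four mentions kept theirs and the sentence is otherwise intact.

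**What to change.** In Appendix 10, Table 1, Grade 2 immediate actions, insert the prefix so that the line speaks of *anti-cytokine therapy*, as the Grade 3 line does. No agent needs to be named and no other section needs to change.

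A clarification letter to sites or the next amendment is enough. The cost is one prefix in one table row, with no change to visits, data collection or sample size.
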